### Objectives

The objective of our study is to evaluate the efficacy of infographics in presenting information, in terms of understanding and remembering research results, compared to standard PLS formats and scientific summary format.

The null hypothesis is that the proportion of the correct answers in all three groups is not going to differ significantly. The equation for that hypothesis is:

$$H_0: \text{Infographic} = \text{PLS} = \text{SciSumm}$$

The alternative hypothesis is that participants in the infographic group (Infographics) will have significantly more correctly answered questions about the topic than those in PLS group (PLS), meaning that infographics enables a better understanding of scientific findings than PLS. Also, the scientific summary group will have the lowest knowledge score of the three groups, meaning that scientific summary is not the suitable way of data presentation about a Cochrane review for lay population. The equation for that hypothesis is:

$$H_a: \text{Infographic} > \text{PLS} > \text{SciSumm}$$

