### Trial design

We will conduct a randomized control trial (RCT) with three different formats of the same systematic review summary (infographics, PLS and scientific summary). The content of these three formats is based on the same systematic review, but the ways of data presentation will differ: visual presentation in plain language, plain language, and scientific language. The trial will be performed at the beginning of the 2016/2017 academic year, with physicians as participants. The trial will be voluntary and anonymous. The survey will consist of 4 parts: 1) demographic data, 2) one format of the summary (randomly assigned), 3) comprehension test

of the information given in the summary, 4) accessibility of information and overall satisfaction with the given summary assessed by survey and 5) health numeracy test. All materials will be in Croatian. The materials used in this research will be assessed by experts in order to confirm face validity of the survey.

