### Outcomes

The results for each participant will be the sum of correct answers at the knowledge test as the primary outcome, while secondary outcomes will be the number of correct answers on health numeracy and the scores on Likert-type scales for accessibility and satisfaction.

a) Demographic characteristics

Participants will first provide information about their gender, age, knowledge about or prior experiences with Cochrane reviews and Cochrane Library, obtained specialization or PhD.

b) Primary outcome: Understanding the information from the review summary

The primary outcome of the study is the score on a knowledge test with ten questions about information contained in all three forms of presentation. The questions will focus on understanding the benefits and risks of the intervention and the quality of evidence described in the systematic review.

Each correctly answered question will be awarded one point, with a maximum of 10 points. Prior research on PLSs (Vandvik et al., 2012) used multiple choice questions with a single correct answer to assess understanding of PLS. However, multiple choice questions are closed questions and the correct answer may provide a visual reminder to the participant and thus do not measure real understanding of the material (Choi & Pak, 2005). In order to reduce this measurement bias, we will use open questions to assess knowledge of the participants.

c) Secondary outcomes

C.1. Reading experience: This section of the survey will include 5 questions about the experience of participants about the text they read, measured on a 10-point Likert type scale, where 1 means *do not agree at all* and 10 means *fully agree*. The total score is the sum of scores on all five answers (maximum 50).

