#### Claiming of the non-inferiority

For the primary outcome, non-inferiority of the experiment format to the control formats will be claimed if the lower limit of the CI (for the difference in average results between intervention group and control groups) is higher than the non-inferiority margin of 20%. The tests of superiority will be applied to the secondary outcomes. We want to perform the non-inferiority testing in order to prove that infographic is no worse than PLS and scientific summaries for information translation in terms of understanding of information. Also, the superiority tests will show that the infographic is better in terms of user satisfaction and accessibility of information compared to standard PLS and scientific summaries.

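### Objectives reads a lowest-of-three knowledge score as showing the scientific summary unsuitable for lay readers; the design supports only a relative conclusion about the physicians enrolled

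*Combined protocol and SAP*

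**What the plan says.** The alternative hypothesis in Objectives has two halves, worded differently. The infographic group "will have significantly more correctly answered questions about the topic than those in PLS group (PLS"), which the plan reads as better understanding. For the other control the plan says "the scientific summary group will have the lowest knowledge score of the three groups, meaning that scientific summary is not the suitable way". The same sentence then makes clear whose needs the verdict concerns: it speaks of "data presentation about a Cochrane review for lay population". The second half drops the word *significantly* and moves from a comparison to a verdict.

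The other sections that bear on that verdict are these:

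- **Outcomes** defines the score: "Each correctly answered question will be awarded one point, with a maximum of 10 points". It names no score as adequate.
- **Inferential statistics** and its Table 1 give an overall Kruskal-Wallis test or ANOVA for understanding. They also mention a possible logistic regression on demographic characteristics.
- **Claiming of the non-inferiority** sets a margin for one family of comparisons only: "non-inferiority of the experiment format to the control formats will be claimed if the lower limit of the CI" for infographic against controls "is higher than the non-inferiority margin of 20" per cent.
- **Trial design** describes a trial "with physicians as participants", and **Eligibility criteria** likewise specifies medical doctors.

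**The concern.** Being lowest of three is a relative fact. Being unsuitable is an absolute judgement, and it needs a standard to be judged against. The plan supplies none: no minimum score, no minimum gap, and no comparison of the scientific summary with the PLS. The verdict also concerns lay readers, whereas the scores come from physicians.

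One of the trial's stated conclusions would therefore not follow from its data even if the ordered hypothesis were fully confirmed. A report written to the plan could dismiss a format that its readers understood well.

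**Working it through.** The plan gives no figure for suitability, so there is none to reproduce. The check is whether any planned result could carry the verdict.

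**1. Is there a standard?** The score runs from 0 to 10 (Outcomes). Outcomes, Sample size, Claiming of the non-inferiority and Inferential statistics name no adequate score. The 40% difference in Sample size is an effect to be detected. The 20% margin applies to the infographic against the controls. Neither is tied to the suitability of the scientific summary.

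**2. Is there a test of the ordering?** A significant Kruskal-Wallis test or ANOVA shows that the three groups are not all alike. It does not show which format is lower than which. The confidence intervals in the non-inferiority section are for infographic minus control. A scientific summary versus PLS comparison of understanding is not planned.

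**3. Would a significant pairwise difference be enough?** Assume 15 completers per group (Sample size) and a common SD. The plan states no SD, so take 1.5 to 3 points as an assumed range. The smallest significant difference between two means is

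t(0.975, 28) × SD × √(2/15) = 2.048 × 0.365 × SD = 0.748 × SD

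- SD 1.5: 1.1 points
- SD 2: 1.5 points
- SD 3: 2.2 points

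At SD 2, compare two illustrative results:

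| | PLS mean | Scientific summary mean | Difference | Significant (above 1.5)? |
|---|---|---|---|---|
| A | 8 | 6 | 2 | yes |
| B | 8 − 4 = 4 | 6 − 4 = 2 | 2 | yes |

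Shifting every score by the same amount changes neither the ranks nor the differences, so both results give the same test statistic. Adequacy does change: readers of the scientific summary answer 6 of 10 correctly in A and 2 of 10 in B. In B the PLS, at 4 of 10, would escape the verdict only because it was not last. Likewise, true means of 9, 8.5 and 8 satisfy the hypothesised order, while readers of the lowest format answer 8 of 10 correctly. A test of order cannot distinguish these cases.

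**4. Does the population match?** The verdict concerns a lay population, but Trial design and Eligibility criteria specify doctors. How well doctors understand a scientific text does not show how well lay people would, even if an adequate score were set.

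**The case against.** The strongest defence is that the sentence is a gloss on a hypothesis, not a decision rule. The null hypothesis speaks of groups not differing significantly, so a test may be implied, and a charitable reader could take the phrase to mean least suitable of the three. Part of this stands: the plan does not say that it will condemn a format on the lowest observed mean alone. But steps 3 and 4 grant the test and still do not reach the verdict, and the wording is absolute as written.

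Three stronger readings are tempting, and the documents do not support them.

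- **A one-in-three error rate.** A reader might infer that, with three equally understood formats, the plan would wrongly call the scientific summary unsuitable in a third of trials. That is only the chance of ranking last under equality. It is not an error rate of this plan, which names an overall test and a null about significant differences. Rank probabilities under a true shortfall would also depend on SDs that the plan does not give.
- **A double standard with the margin.** The non-inferiority section aims, "in order to prove that infographic is no worse than PLS and scientific summaries", to allow the infographic some shortfall. A reader might infer that the same shortfall is acceptable in one format and disqualifying in another. But the margin covers only the infographic against controls, carries no sign, and applies to a confidence limit. Read it as −2 points on the 10-point scale, with a two-sided 95% interval and SD 2 (all assumptions). An observed infographic shortfall of 1 point then has a lower limit of −1 − 1.5 = −2.5 and fails. Only shortfalls below about 2 − 1.5 = 0.5 points would pass.
- **Using the margin as a suitability threshold.** Requiring the scientific summary to fall more than 20% below the PLS would be another relative comparison. It would set no adequate score and would still rest on physicians' answers.

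One caveat concerns the population. Participant timeline and Sequence generation describe students, in conflict with Trial design and Eligibility criteria. If non-medical students were enrolled, the mismatch with lay readers would be smaller, but the step from order to suitability would remain unsupported.

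**Conclusion.** The point holds and is minor. Objectives draws an absolute conclusion about lay readers from a relative result in physicians. No adequacy level, minimum gap or scientific summary versus PLS comparison is specified. Full confirmation of the ordered hypothesis would support only the statement that the scientific summary was less well understood by those who took part.

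This affects one interpretive clause. It changes no sample size, data collection or existing analysis. The argument rests on the text and needs no assumed SD; the SDs above serve only to illustrate it. The population part relies on Trial design and Eligibility criteria as the governing definition of participants.

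**What to change.** In Objectives, replace the suitability clause with a relative conclusion limited to the participants, for example: *the scientific summary was less well understood than the PLS by the participating physicians*. State that this will be concluded only if the scientific summary versus PLS difference in knowledge score is statistically supported. Add that comparison to Inferential statistics and report the difference with its confidence interval whatever the result. Make no suitability verdict, for lay readers or otherwise.

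The cost is a change of wording and one pairwise estimate from data already being collected. The downside is a more modest conclusion about the scientific summary.

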### Trial design

We will conduct a randomized control trial (RCT) with three different formats of the same systematic review summary (infographics, PLS and scientific summary). The content of these three formats is based on the same systematic review, but the ways of data presentation will differ: visual presentation in plain language, plain language, and scientific language. The trial will be performed at the beginning of the 2016/2017 academic year, with physicians as participants. The trial will be voluntary and anonymous. The survey will consist of 4 parts: 1) demographic data, 2) one format of the summary (randomly assigned), 3) comprehension test

of the information given in the summary, 4) accessibility of information and overall satisfaction with the given summary assessed by survey and 5) health numeracy test. All materials will be in Croatian. The materials used in this research will be assessed by experts in order to confirm face validity of the survey.

## **Methods: Participants, interventions, and outcomes**

### Setting and recruitment

The trial will be performed online using SurveyMonkey software (A/B testing method).

### Eligibility criteria

Eligible participants will be medical doctors in any specialty or field of work. Authors will make a list of publicly available e-mail addresses of doctors—clinical researchers from the School of Medicine and University Hospital Center in Split to make an email list of potential participants

### Interventions

Infographics format of a Cochrane systematic review summary represents the experimental intervention in the trial. The control groups will receive either PLS (which represent text format with simple explanation of the survey topic main findings and is intended for lay audience) or the scientific summary (the text written for the academic population and practitioners) groups. We will use formats already available for the systematic review on external cephalic version for breech presentation before term (Hutton et al, 2015.).

All three types of Cochrane summaries will be translated into Croatian by the trial organizers, and back translated to English by an independent language expert to ensure the quality of the Croatian translation. The survey instrument will be in Croatian.

### Outcomes

The results for each participant will be the sum of correct answers at the knowledge test as the primary outcome, while secondary outcomes will be the number of correct answers on health numeracy and the scores on Likert-type scales for accessibility and satisfaction.

a) Demographic characteristics

Participants will first provide information about their gender, age, knowledge about or prior experiences with Cochrane reviews and Cochrane Library, obtained specialization or PhD.

b) Primary outcome: Understanding the information from the review summary

The primary outcome of the study is the score on a knowledge test with ten questions about information contained in all three forms of presentation. The questions will focus on understanding the benefits and risks of the intervention and the quality of evidence described in the systematic review.

Each correctly answered question will be awarded one point, with a maximum of 10 points. Prior research on PLSs (Vandvik et al., 2012) used multiple choice questions with a single correct answer to assess understanding of PLS. However, multiple choice questions are closed questions and the correct answer may provide a visual reminder to the participant and thus do not measure real understanding of the material (Choi & Pak, 2005). In order to reduce this measurement bias, we will use open questions to assess knowledge of the participants.

c) Secondary outcomes

C.1. Reading experience: This section of the survey will include 5 questions about the experience of participants about the text they read, measured on a 10-point Likert type scale, where 1 means *do not agree at all* and 10 means *fully agree*. The total score is the sum of scores on all five answers (maximum 50).

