#### Inferential statistics

The primary outcome of the trial understands of research results presented in various summary formats by lay persons. Each question has a single possible answer and the participant's result is the sum of the correct answers. Also, it is possible to determine how each one of the demographic characteristics predicts correct answer on the knowledge test using logistic regression.

For overall reading experience and accessibility of information between group testing we plan to test the distributions of the variables, and then to choose the non-parametric test (Kruskall-Wallis test) if the distribution of results is not normal or to choose the parametric test (ANOVA) if the distribution of results is normal.

Table 1 Overview of the outcome measures

Outcome	Scale	Measure	Methods of analysis
Understanding	Dichotomous	Sum of correct answers	Kruskall-Wallis/ANOVA
Accessibility of information	Continuous	Likert-type scale from 1 to 10	Kruskall-Wallis/ANOVA
Reading experience	Continuous	Likert-type scale from 1 to 10	Kruskall-Wallis/ANOVA
Health numeracy	Dichotomous	Sum of correct answers	Kruskall-Wallis/ANOVA; Spearman correlation coefficient with understanding outcome

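### The primary format comparison makes no use of the prior Cochrane experience and PhD/specialization data recorded before exposure; one or two pre-specified covariates could improve precision at small cost

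*Combined protocol and SAP*

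**What the plan says.** - **Baseline data.** Outcomes, part a, has participants begin with gender, age and "knowledge about or prior experiences with Cochrane reviews and Cochrane Library, obtained specialization or PhD". The Trial design section also lists demographics ahead of the summary.
- **Primary outcome.** "The primary outcome of the study is the score on a knowledge test with ten questions", scored 0 to 10.
- **Primary analysis.** Table 1 under Inferential statistics gives "Kruskall-Wallis/ANOVA" for understanding. The section on claiming non-inferiority uses a confidence interval "for the difference in average results between intervention group and control groups", and the claim is made if its lower limit "is higher than the non-inferiority margin of 20" per cent. Neither place names a covariate.
- **Allocation.** Sequence generation describes permuted blocks and names no stratification factor.
- **Other use of the baseline data.** They are described by group. Inferential statistics adds that "it is possible to determine how each one of the demographic characteristics predicts correct answer on the knowledge test using logistic regression". That model is optional and has no term for format, so it does not adjust the format comparison.
- **Population and size.** Eligible participants are "medical doctors in any specialty or field of work". The Sample size section asks for at least 15 completers per group.

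**The concern.** The test asks about benefits, risks and quality of evidence in a Cochrane review of external cephalic version. Doctors from any field may differ in how familiar they are with Cochrane reviews and research evidence, so prior Cochrane experience or a PhD could plausibly relate to the score. If so, two things follow in a small trial. First, score variation that could be explained stays in the error term and widens the confidence interval set against the margin. Second, arms of about 15 will often differ by chance on such a variable. Neither the allocation nor the analysis deals with this, and a reader of the baseline table could not tell how far an observed format difference reflects it.

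If covariates are not named in advance, any later adjustment would also be a choice made among several collected variables after the data are seen.

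**Working it through.** **The plan's own figure.** The Sample size section gives 15 per group for a 40-point difference. The usual two-sided pooled formula for 80% against 40% (alpha 0.05, power 80%) gives 23 per group; 80% against 30% gives 15. No SD for the score is given, so the planned precision on the 0-10 scale cannot be reproduced. The check below takes 15 per group as it stands and does not depend on how it was reached.

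**Inputs from the documents.** Three formats; minimum n = 15 per arm, so N = 45 (equal allocation assumed); score 0-10; margin 20%.

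**Assumptions.** The margin is read as a permitted shortfall of 2 points out of 10. SD of the score is 2. The true difference is zero, and the interval is a two-sided 95% interval for one pairwise comparison. R is the multiple correlation of the chosen covariates with the score within arms. The documents give neither R nor the SD.

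**Variance of a format difference.** With k covariate degrees of freedom, adjusted relative to unadjusted variance is

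ratio = (1 − R²) × (N − 4)/(N − 4 − k) = (1 − R²) × 41/(41 − k).

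The second factor is the cost of estimating the covariate effects. Adjustment breaks even at R² = k/41: about 2% for k = 1, 5% for k = 2 and 7% for k = 3.

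**Power.** SE = 2 × √(2/15 × ratio). Power comes from the noncentral t distribution with noncentrality 2/SE and 42 − k degrees of freedom. Unadjusted: SE = 2 × √(2/15) = 0.730, noncentrality 2.74, 42 df, power 76%. Example with k = 1 and R = 0.4: ratio = 0.84 × 41/40 = 0.861, SE = 0.678, noncentrality 2.95, 41 df, power 82%.

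| Covariates | R = 0 | R = 0.3 | R = 0.4 | R = 0.5 |
|---|---|---|---|---|
| 1 | 75% | 79% | 82% | 86% |
| 2 | 74% | 78% | 81% | 85% |
| 3 | 73% | 77% | 80% | 84% |

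In variance terms, one covariate gives ratios of 1.025, 0.933, 0.861 and 0.769 across the columns; two give 1.051, 0.957, 0.883 and 0.788.

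**Dependence on the SD.** The same formula with SD 2.5 gives 57% unadjusted. With one covariate it gives 56% at R = 0 and 68% at R = 0.5. The pattern holds: a loss of about one point if the covariate is useless, and a gain of about ten if it is strong.

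**Chance imbalance.** For a yes/no covariate with assumed prevalence 30-50% and 15 per arm, exact binomial calculation (simple randomisation) gives a 32-36% chance that two given arms differ by at least 20 percentage points (3 of 15), and 7-10% for at least 33 points (5 of 15). By simulation, the chance that some pair of the three arms differs by at least 20 points is 58-63%. If the covariate were worth 2 points on the score (assumed), a 20-point imbalance would move the observed format difference by 0.20 × 2 = 0.4 points, one fifth of a 2-point margin.

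**The case against.** An unadjusted comparison in a small randomised trial is a legitimate choice. Several arguments support leaving it alone.

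- **Validity.** A reader might infer that uncorrected imbalance biases the comparison or inflates type I error. It does not: randomisation makes the unadjusted test valid across all possible allocations, and the planned baseline description would make imbalance visible. This stands, and it limits the point to precision and credibility.
- **Unknown prediction.** A reader might infer that the plan itself expects these variables to predict the score strongly. It says only that "it is possible to determine how each one of the demographic characteristics predicts correct answer on the knowledge test" and gives no estimate. With several weak covariates, adjustment loses precision. This stands, and it is the reason for using one or two covariates rather than three or more.
- **Specialty.** It is tempting to argue that obstetricians will know the answers and that adjusting for obstetrics would remove this with data in hand. The listed item may record only whether a specialization was obtained, not which one. Even if it records the field, that cell could be very small among 45 doctors.
- **Size.** Fifteen is a minimum. With more recruits, both the imbalance and the cost of a covariate shrink.
- **Model form.** A linear model on a bounded score sets aside the rank-based option in Table 1. Keeping the planned analysis as sensitivity answers this. The non-inferiority rule also already needs a mean difference with a confidence interval, which Kruskal-Wallis does not supply.

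**Conclusion.** The point holds as an efficiency improvement, not as an error. The primary comparison is unadjusted, suitable pre-exposure variables are recorded, and neither the allocation nor the analysis uses them. At N = 45, with SD 2 and a 2-point margin assumed, one covariate raises power from 76% to between 79% and 86% if its correlation with the score is 0.3 to 0.5; two raise it to between 78% and 85%. If they are unrelated to the score, the loss is one to two percentage points. No figure in the documents fixes where in that range the trial lies. The documents do not support calling the planned test biased, describing these variables as strong predictors, or treating an obstetrics indicator as already available.

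**What to change.** Add to Inferential statistics that the primary analysis is a linear model of the 0-10 score on format plus one or two named covariates recorded before the summary. The first is prior Cochrane experience (yes/no). A second could be PhD (yes/no), or relevant specialization only if the survey records which specialization. Check the exact coding against the questionnaire before fixing the choice.

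Take the format differences and 95% confidence intervals for the 20% margin from this model. Keep the planned unadjusted ANOVA/Kruskal-Wallis as sensitivity analysis. State that health numeracy is not a covariate: it is a secondary outcome placed last in the survey, after the summary.

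The cost is a sentence or two of text, no new data if the items are coded as assumed, and one or two degrees of freedom out of 42. The statistical downside is a fall in power from 76% to about 75% (one covariate) or 74% (two) if the covariates do not predict the score.
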